6. DRUGS/ SUBSTANCES/ DEVICES

- **The rationale for choosing the drug and dose or for choosing the device to be used.**

Nicotine and non-nicotine pharmacotherapy to treat tobacco addiction will be prescribed in Epic by [name] [PI], Medical Director of the Tobacco Treatment Clinic at Bayview Medical Center. [name] is a faculty member in the Division of Pulmonary Critical Care & Medicine.

Pharmacotherapy oversight will also be led the PI, an expert in pharmacotherapy for tobacco dependence and smoking cessation.

The selection and prescription of pharmacotherapies will approximate an approach currently employed the PI. The PI currently provides medical care in two public housing complexes in Baltimore: Monument East and McColloch Homes.

Patients will undergo a multistep process to screen and monitor adverse effects on therapy. The medications chosen based on initial screening will be prescribed and delivered to participants. Prior to initiating the administration of the medications, participants will again be evaluated for the presence of absolute or relative contraindications of the prescribed pharmacotherapy regimen (BASELINE VISIT: Time Point 3). Participants will be provided a 24-hour contact phone number to report concerns or adverse effects on therapy. All concerns will be reviewed by the PI within 24 hours of receipt.

All pharmacotherapy is FDA approved and dosing will be based on FDA drug labelling.

- NRT gum or lozenge:

Baseline to end of study = 4 weeks	
STEP 1	Determine dosage
Do you smoke your 1 st cigarette within 30 minutes of waking up?	
Yes → Use 4 mg gum or lozenge	
No → Use 2 mg gum or lozenge	
STEP 2	Frequency of administration
Take the recommended dose (1-piece) by mouth every 1-2 hours	

- NRT patch:

Baseline to end of study = 4 weeks	
STEP 1	Determine dosage

Date: 01/10/2024

Principal Investigator: [name]

Application Number: IRB00224186

Do you smoke \geq 10 cigarettes per day? Yes \rightarrow Use 21 mg patch No \rightarrow Use 14 mg patch
STEP 2 Frequency of administration
Apply one new patch per day

- Chantix®:

Baseline to end of study = 4 weeks
STEP 1 Dosing & administration
Day 1 – 3: 0.5 mg by mouth daily Day 4 – 7: 0.5 mg by mouth twice-daily Day 8 – 30: 1 mg by mouth twice-daily

- Justification and safety information if FDA approved drugs will be administered for non-FDA approved indications or if doses or routes of administration or participant populations are changed.

Not applicable

- Justification and safety information if non-FDA approved drugs without an IND will be administered.

Not applicable

7. STUDY STATISTICS

a. Primary outcome variable

The primary endpoint will be study feasibility. Feasibility will be measured using open-ended questions administered by the research team and targeting the study stakeholders (study participants, community stakeholders and research team). The answers will serve as a means to evaluate the need for further modification in the recruitment, screening, consent, study implementation and evaluation phases of future study testing..

b. Exploratory outcome variables

Pre- & post-changes in nicotine dependence levels – Results will be stratified by baseline smoking behaviors, sociodemographic characteristics and socioeconomic stressors. For group-wise comparisons, t-test or analysis of variance will be used. Regression analyses will be performed to investigate the relationship between baseline measures and changes in smoking characteristics as the pilot study progressed.

c. Statistical plan including sample size justification and interim data analysis

Date: 01/10/2024

Principal Investigator: [name]

Application Number: IRB00224186

This study will not be powered for significance. The primary purpose of this study is to assess feasibility of the pilot study design.

d. Early stopping rules

Not applicable

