8. Pregnant – women will verbally acknowledge that they are *not* pregnant or trying to become pregnant in the next 8 weeks from the time of screening and recruitment to ensure no intake of nicotine and non-nicotine pharmacotherapy
9. Breastfeeding – women who are verbally acknowledge they are breastfeeding will be excluded from the study. This exclusion factor is in place secondary to breastfeeding concerns associated with the study’s usage of nicotine and non-nicotine pharmacotherapy
10. Ongoing participation in a tobacco cessation program or related tobacco intervention study. Past participation in previous iterations of the protocol is not an exclusion criteria.
11. No active health insurance.
12. Unable to verbally state that they are willing to reduce or quit smoking upon recruitment and screening
13. Adults lacking capacity to consent
14. Non-English speakers
15. Self-reported usage of *only* non-combustible tobacco products, such as smokeless tobacco or Electronic Nicotine Delivery Devices (ENDS).

Date: 01/10/2024

Principal Investigator: [name]

Application Number: IRB00224186

16. Anticipated relocation outside of Douglass or Brooklyn Homes prior to the final study visit
17. Clinical condition(s) that serve as absolute contraindications for the usage of NRT and non-NRT products and non-NRT products (Chantix®) (Reference: PMID 36280333)
 - a. Absolute contraindications of NRT products:
 - *NRT gum: Dysphagia and subsequent aspiration risk*
 - *NRT lozenge: Dysphagia and subsequent aspiration risk*
 - *NRT transdermal patch: Severe diffuse skin disease*
 - *Women who are pregnant or breastfeeding.*
 - b. Absolute contraindication of Chantix®:
 - *Inability to swallow pills*
 - *History of serious hypersensitivity or skin reactions to Chantix®*
 - *Women who are pregnant or breastfeeding*

***NOTE 1:** We will cease enrollment at 60 participants. Our aim is to enroll 30 participants at Douglass Homes and 30 participants at Brooklyn Homes. We anticipate that ≈20% of screened participants (12 people) will not continue participation at the start of the intervention. This allows enrollment and follow-up of 48 participants.

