(see Preliminary data). Based on the low frequency of observed side effects, there is a very low likelihood of a participant not being a good candidate for NRT patch (“controller”) or NRT gum/lozenge (“acute”). This means that an individual who may not qualify for “Chantix” could be converted “NRT transdermal patch”, while continuing on their NRT gum/lozenge.

TIME POINT 4 – follow/up visit

WEEKLY FOLLOW-UP VISIT

Each weekly follow-up visit will occur remotely based on participant preference for a videoconference platform (Zoom) or mobile phone. Two separate times for study visit will be offered to allow participants the option to choose a time more preferable to their schedule. If Zoom is not preferable or communication issues arise, standard audio phone-based options without video capacity will be instituted. There will be NO video or audio recordings of any of the study visits. Paper or electronic copies of participant answers will be stored in CRMS.

The intervention at these follow-up visits will have 4 key features:

1. Survey completion that contains questions about interval smoking characteristics (see “Supplementary Document3”).
2. Pharmacotherapy education that reinforces appropriate medication administration and commonly observed side effects. ***See Drugs/Substances/Devices and Risks sections in this protocol for more information on side effects.***
3. Cessation-directed motivational interviewing

1ST STEP – CONFIRMATION AND SURVEY SCREENING

- Participants will check-in with research staff to confirm that they were enrolled at the baseline study event (Week 0).
- A short survey (approximately 5 minutes) will be undertaken to acquire key smoking characteristics (see “Supplementary Document3”). The survey will ask about the usage of the prescribed pharmacotherapies and possible explanations for non-optimal adherence. The survey will also query the degree of nicotine dependence. The study follow-up visits are using shortened surveys to capture immediately relevant study outcomes, reduce study fatigue, and to improve participant acceptability of the project.

Surveys will be displayed on the video conference call if Zoom is the preferred modality for the study. For participants with difficulty reading the survey, the questions will be read aloud and the responses will be recorded. For phone-based visits, our research team will read the questions aloud and record the answer choices.

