All elements of this time point mirror the description represented above (TIME POINT 4). The only difference is that one interval text messaging type will be used. *We will no longer ask Chantix® users about medication concerns every 72 hours, if they have not reported any adverse effects to date on therapy.* Participants will continue to receive reminders at 72 hours and 24 hours prior to the next scheduled follow-up study visit.

TIME POINT 6 – follow/up visit

WEEKLY FOLLOW-UP VISIT

All elements of this time point mirror the description represented above (TIME POINT 5)

TIME POINT 7 – FINAL follow/up visit

FINAL VISIT

This final study visit will occur by videoconference (Zoom) or a phone call. Two separate times for the study visit will be offered to allow participants the option to choose a time more

Date: 01/10/2024

Principal Investigator: [name]

Application Number: IRB00224186

preferable to their schedule. The intervention at this time point will have 3 key features:

1. Survey completion that contains questions about smoking characteristics and completion of open-ended questions that explore the feasibility of the study pilot (see “Supplementary Document 3”).
2. Referral to [name] or Tobacco Treatment Clinic at Bayview Medical Center if continued smoking cessation resources are requested
3. \$15 cash equivalent reimbursement for study participation.

1ST STEP – CONFIRMATION AND SURVEY SCREENING

- Participants will check-in with research staff to confirm their enrollment in the study.
- A short survey (approximately 5 minutes) will be undertaken to acquire key smoking characteristics (see “Supplementary Document 3”). The survey will ask the usage & frequency that the prescribed pharmacotherapies are being used, as well as query the degree of nicotine dependence over the 4-week pilot period. Surveys will be displayed on the video conference call if Zoom is the preferred modality for the study. For participants with difficulty reading the survey, the questions will be read aloud and the responses will be recorded. For phone-based visits, our research team will read the questions aloud and record the answer choices.

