Patients will undergo a multistep process to screen and monitor adverse effects on therapy. The medications prescribed & delivered based on initial screening will only be recommended for administration after participants undergo confirmation of appropriateness of drugs selection at the time of the baseline study visit (WEEK 3). Participants will be provided a 24-hour contact phone number to report concerns or adverse effects on therapy. All concerns will be reviewed by the PI within 24 hours of receipt.

All adverse events will be followed until resolution, stabilization, or until it has been determined that the study intervention or participation is not the cause. Further action and/or candidacy for an alternative pharmacotherapy (e.g. Chantix® changed to NRT patch) will occur under the direction of the medical specialists (PI).

Date: 01/10/2024

Principal Investigator: [name]

Application Number: IRB00224186

We will also ensure that Chantix is being administered to the correct participants and drug education is being delivered at each study visit through the completion of medication dispensing form (**see “Supplementary Document 5”**). The form requires the signature of the study team member who will verify administration and education of the medication to the correct participant.

c. Plan for reporting unanticipated problems or study deviations

All unanticipated problems and study deviations will be reviewed by the PI [name].

We have built the protocol to accommodate minor deviations. For example, our protocol is still maintained despite participants unable to attend the study visits or if all outcomes are not obtained during the 4 week trial. These will be reported in an IRB continuing review.

Major deviations will be reported immediately to the IRB. A major deviations are events that cause or could cause harm to subjects or others or that affect the fidelity of our research.

d. Legal risks such as the risks that would be associated with breach of confidentiality

Not applicable

e. Financial risks to the participants

There are no financial risks for participants

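### Dependence is asked at every weekly visit but analysed as a two-point change, so without imputation anyone lacking a final survey is left out; a mixed model would use all visits

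*Combined protocol and SAP*

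**What the plan says.** Section 7b (exploratory outcome variables) defines the outcome as the change in nicotine dependence from before to after the intervention. Three sentences on analysis follow: "Results will be stratified by baseline smoking behaviors, sociodemographic characteristics and socioeconomic stressors"; "For group-wise comparisons, t-test or analysis of variance will be used"; and "Regression analyses will be performed to investigate the relationship between baseline measures and changes in smoking characteristics as the pilot study progressed". The section names no test for the overall change, no analysis set, no rule for missing surveys and no repeated-measures model. Section 7c adds "This study will not be powered for significance", and the primary endpoint in 7a is feasibility.

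On data collection, Section 4, Time Point 4, first step, states "The survey will also query the degree of nicotine dependence". Time Point 5 is described as mirroring Time Point 4, and Time Point 6 as mirroring Time Point 5. The final visit (Time Point 7) asks about dependence again. The baseline text names only smoking characteristics, but a pre-post change implies a baseline dependence score.

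On missing data, Section 8c treats the protocol as maintained when participants miss visits or "if all outcomes are not obtained during the 4 week trial". Time Points 3 and 4 (fourth step) say that participants disenrolled because both medications were stopped will be phoned at the end for the final survey.

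**The concern.** The schedule gives up to five dependence scores per person: baseline, three weekly visits and the final visit. The outcome in Section 7b uses two of them. Someone who attends baseline and two weekly visits and is then lost has given three usable scores. A pre-post change cannot use any of them unless a final value is filled in, and the plan mentions no imputation.

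The stake is an estimate of change that rests on people who reached the end, less precise than the collected data allow and possibly not representative of those who started. Dependence change is the only quantitative outcome named in Section 7, and the protocol says that the findings will inform larger studies. It is still exploratory, and no decision in the documents depends on it.

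**Working it through.** **1. The plan's own figure.** Section 4, Time Point 1, Note 1 caps enrolment at 60 and expects about 20% (12 people) not to continue at the start of the intervention. 60 × (1 − 0.20) = 60 − 12 = 48. This reproduces the stated 48.

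**2. How many would lack a final score.** The documents give no retention figure for the intervention phase of this study. The earlier on-site pilot (Section 3) reports 79.5% at the final week. (79.5% of 40 is 31.8, not a whole number; 31/39 gives 79.5%, so its denominator may be 39.) Using 79.5% as an assumption, with an assumed range around it:

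| Retention | With final score | Without |
|---|---|---|
| 90% (assumed) | 48 × 0.90 = 43.2 | 4.8 |
| 79.5% (earlier pilot) | 48 × 0.795 = 38.2 | 9.8 |
| 70% (assumed) | 48 × 0.70 = 33.6 | 14.4 |

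The central case is about 38 with a final score and 10 without. Phone contact with disenrolled participants would lower the 10.

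**3. Direction of bias.** With retention r, the completers' mean change differs from the mean for all starters by (1 − r) × (completers' change − leavers' change). At r = 0.795 the factor is 0.205. If completers improve by 0.8 unit more than leavers, the result is too favourable by 0.205 × 0.8 = 0.164 unit. If they improve by 0.8 less, it is too unfavourable by the same amount. The documents give neither the size nor the sign of that difference.

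**4. What a model over all visits would gain.** I simulated 1,000 trials per setting with 48 people, baseline plus four follow-up scores, and about 20–22% lost by the final visit. None of the following assumptions comes from the documents:

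- The true change is −0.50 SD of a single score.
- Correlation between visits is exchangeable at 0.5, exchangeable at 0.7, or autoregressive at 0.8.
- Loss is completely at random (MCAR), more likely after a high last observed score (MAR), or more likely with a high unseen score (MNAR).

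The model had categorical visits and a known covariance. Entries are mean change for the three correlation settings in order, with the standard error (SE) in brackets.

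| Loss | Completers' change | All-visit model |
|---|---|---|
| MCAR | −0.499 (0.166), −0.500 (0.127), −0.500 (0.182) | −0.497 (0.160), −0.499 (0.122), −0.501 (0.169) |
| MAR | −0.474 (0.164), −0.477 (0.123), −0.471 (0.179) | −0.503 (0.159), −0.496 (0.118), −0.502 (0.171) |
| MNAR | −0.532 (0.169), −0.522 (0.124), −0.536 (0.179) | −0.575 (0.163), −0.553 (0.122), −0.570 (0.168) |

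- **MCAR:** neither is biased. SE ratios are 0.160/0.166 = 0.96, 0.122/0.127 = 0.96 and 0.169/0.182 = 0.93, so the model's SE is about 4–7% smaller. Complete follow-up would do somewhat better: √(48/38) = 1.124, so having 38 instead of 48 raises the SE by about 12%.
- **MAR:** completers understate the change by 0.02–0.03 SD; the model does not.
- **MNAR:** both overstate the change, and the model is further from the truth.

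A known covariance favours the model. With an estimated unstructured covariance (150 runs only), the MCAR standard errors were 0.155, 0.128 and 0.185. The precision gain at n = 48 may therefore be smaller than 4–7%, or absent.

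**The case against.** The strongest reply is that the plan never states a completers-only rule. The t-test sentence governs comparisons between baseline groups, not the overall change. The regression sentence promises an analysis of change as the study progressed and may use the weekly scores. One group of early leavers is to be phoned for the final survey. The outcome is exploratory in an unpowered feasibility pilot. The proposed model also assumes that one dependence measure is comparable across visits, whereas follow-up uses shortened surveys and the final survey asks about the whole four weeks.

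Much of this stands. Four stronger readings are tempting, and the documents do not support them:

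- **That the plan discards every early leaver.** Exclusion is the default consequence of a change score without imputation; it is not a stated rule. Disenrolled participants who are reached by phone would have a final value.
- **That the result will overstate benefit.** The sign depends on who leaves (step 3), and in the MAR simulation completers understated it.
- **That an unpaired test is planned for the pre-post change.** No test is named for the overall change.
- **That a site term must be added because enrolment is planned by site ("Our aim is to enroll 30 participants at Douglass Homes and 30 participants at Brooklyn Homes").** A site main effect alone does not adjust the change; that would need site-by-visit.

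What the reply does not answer is how a person with weekly scores but no final survey enters the change analysis. The regression sentence names no model, time structure or missing-data handling. The phone call covers only those for whom both medications are stopped, which the protocol does not expect to happen, so people lost to contact remain missing.

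**Conclusion.** The point holds as a low-priority improvement to an exploratory analysis. Section 7b defines a two-point change while the schedule collects dependence at every follow-up visit and missing outcomes are expected. Unless a final value is imputed, people without a final survey are left out of that change and their weekly scores are unused.

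About 10 of 48 starters would be affected if the earlier pilot's retention recurred, or about 5 to 14 over the assumed range of 90% to 70%. Phone contact with disenrolled participants would reduce these numbers. The direction of any bias is unknown.

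The gain from using all visits is modest: at best a standard error about 4–7% smaller, or 0.02–0.03 SD of bias removed if loss depends on observed scores. Both figures rest on simulation inputs that the documents do not give. There would be no correction for loss that depends on unseen scores. The primary feasibility endpoint is unaffected.

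**What to change.** In Section 7b, estimate the week-4 change in dependence with one linear mixed model over baseline and all follow-up visits at which the same dependence measure is collected. Use visit as a categorical fixed effect and a participant random effect. Include everyone with a baseline score. Report the week-4 change with a 95% CI and the number of participants with data at each visit. Confirm from the survey documents that the dependence items match across visits, including the end-of-study phone survey.

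Limit baseline-by-visit interactions to a few characteristics named in advance, with site-by-visit among them if site is of interest. With five visits, each binary characteristic adds four interaction parameters, and at most 48 people cannot support many.

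The cost is a few sentences and a little more analysis work, with no new data collection. The model assumes that missingness depends on observed values. It adds little for people with only a baseline score and cannot recover the roughly 12 people expected to be lost before baseline.

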 - Participants will complete baseline surveys that capture sociodemographic and smoking characteristics (see “Supplementary Document 3”). Participants will be allowed sufficient time (no limit) to complete the survey. For participants with difficulty reading the survey, the questions will be read aloud and the responses will be recorded. We anticipate that the survey will take no more than 5-10 minutes to complete since we purposely are acquiring fewer but impactful questions to minimize participant study burden.
- RE-confirmation of any potential contraindications for the prescribed NRT and non-nicotine pharmacotherapies – as chosen during screening. This review of contraindications will occur by our research team.

This step will duplicate the review of absolute and relative contraindications undertaken during the screening process:

- Absolute contraindications of NRT products
 - *NRT gum: Dysphagia and subsequent aspiration risk*
 - *NRT lozenge: Dysphagia and subsequent aspiration risk*
 - *NRT transdermal patch: Severe diffuse skin disease*
 - *Women who are pregnant or breastfeeding.*
- Relative contraindication of non-NRT products:
 - *Recent myocardial infarction (≤ 2 weeks), arrhythmias, angina, ulcers, uncontrolled high blood pressure, overactive thyroid, pheochromocytoma, or a dental condition or disorder.*
- Absolute contraindication of Chantix®:
 - *Inability to swallow pills*
 - *History of serious hypersensitivity or skin reactions to Chantix®*
 - *Women who are pregnant or breastfeeding*

- Relative contraindication of Chantix®:
 - Severe renal impairment (dosage adjustment is necessary)
 - Underlying neuropsychiatric disease
- ***NOTE:** If contraindications are noted, the team will immediately review them with the study's advanced practice provider (physician and/or pharmacist). If contraindications exist and the medical specialists determine the patient is not a suitable candidate any longer for the prescribed pharmacotherapies, the patient will be disenrolled from the study; they will be provided contact information of local smoking cessation resources ([name] and Tobacco Treatment Clinic at Bayview Medical Center). Modifications in acute and controller therapy dosing may be employed in conversations with our team's medical specialists (e.g., transdermal NRT patch in replacement of Chantix®).

2ND STEP – DRUG EDUCATION AND SIDE-EFFECT MONITORING

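### Section 7b leaves room to test change in a smoking or dependence measure against that measure's own baseline, where regression to the mean alone makes heavier smokers seem to improve more (minor, exploratory only)

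*Combined protocol and SAP*

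**What the plan says.** Section 7b is the whole analysis text for change. For pre-to-post change in nicotine dependence it says "Results will be stratified by baseline smoking behaviors, sociodemographic characteristics and socioeconomic stressors", and then "For group-wise comparisons, t-test or analysis of variance will be used". For smoking characteristics more widely it says "Regression analyses will be performed to investigate the relationship between baseline measures and changes in smoking characteristics as the pilot study progressed". It does not list the baseline measures or name the dependence instrument.

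The data collection is in section 4. At Time Point 3, "Participants will complete baseline surveys that capture sociodemographic and smoking characteristics". At the weekly visits (Time Point 4, mirrored at 5 and 6), "The survey will also query the degree of nicotine dependence". The final survey at Time Point 7 will "query the degree of nicotine dependence over the 4-week pilot period". The survey items are referred to Supplementary Document 3, which is not part of the supplied text.

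Section 4 describes a pre-post design without a comparator. Note 1 on enrolment says "This allows enrollment and follow-up of 48 participants", and section 7c says "This study will not be powered for significance".

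**The concern.** Smoking characteristics are measured at baseline and again later. The plain meaning of baseline measures, or of baseline smoking behaviors, therefore includes the starting value of the outcome itself. Change is the later value minus the baseline value, so error in the baseline appears in the predictor with a plus sign and in the outcome with a minus sign. A participant who scores high at baseline partly by chance will tend to score lower next time, with or without any effect of treatment.

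The result would read as greater benefit in heavier or more dependent smokers. The data-management text in section 4 says that findings will be used to develop larger studies, so such a result could influence whom a later trial targets. This is a bias in the estimate and not only a lack of precision, so the statement in 7c that the study is unpowered does not answer it.

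**Working it through.** **Sample size.** Note 1 gives 60 enrolled and about 20% not continuing: 60 x 0.20 = 12, and 60 - 12 = 48. The plan's figure is reproduced, and n = 48 is used below.

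**Assumptions not in the documents.** Reliability R of 0.7, 0.8 or 0.9; normal scores; equal error variance before and after; two-sided 5% test.

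**Model.** pre = T + e0 and post = T + d + e1, where T is the true level (SD 1), d is true change independent of T, and e0 and e1 are independent errors. R = Var(T) / (Var(T) + Var(e)).

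**Slope of change on own baseline.** Cov(post - pre, pre) = Cov(d + e1 - e0, T + e0) = -Var(e). Dividing by Var(pre) gives -Var(e) / (Var(T) + Var(e)) = -(1 - R). At R = 0.8, Var(e) = 0.25 and the slope is -0.25 / 1.25 = -0.20. Neither n nor the spread of d enters.

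**Median split on own baseline.** In large samples the upper half appears to fall by 1.596(1 - R) baseline SD more than the lower half. The table shows the simulated value at n = 48.

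| | R = 0.7 | R = 0.8 | R = 0.9 |
|---|---|---|---|
| Slope from noise alone | -0.30 | -0.20 | -0.10 |
| Gap between halves (baseline SD) | 0.47 | 0.31 | 0.16 |
| Regression falsely significant, identical true change | 79% | 60% | 34% |
| Same, true change SD 1.0 | 44% | 24% | 10% |
| Split t-test falsely significant, identical true change | 58% | 41% | 23% |
| Same, true change SD 1.0 | 30% | 17% | 8% |

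**Other stratifiers (split t-test, identical true change).**
- One item of an assumed six-item dependence score: 27 / 23 / 16%. With three items it is 39 / 31 / 20%, and with ten 19 / 17 / 14%.
- A different baseline measure with independent error: 4.7 to 5.1%, the nominal level.
- A different measure whose error correlates with that of the outcome: 6.0 to 8.0% at correlation 0.25, and 8.9 to 18.5% at 0.5.

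**If heavier smokers really do cut down more.** If everyone truly falls by 30% of their own level, the slope is -0.3R - (1 - R) = -0.51 / -0.44 / -0.37. At R = 0.8 that is -0.24 real and -0.20 noise. Two time points alone do not separate the parts.

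**Using the later visits.** The trend over weeks 1 to 4 does not contain the baseline value. With independent errors and linear true change unrelated to true baseline, regressing that trend on baseline gave a mean slope of 0.00 and about 5% false positives at each reliability. Under the 30% proportional reduction it recovered a negative slope, with power from 19 to 87% depending on the setting. It does not detect a differential drop completed before week 1.

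**The case against.** The strongest reply is that the faulty analysis is not in the plan. Section 7b never says that change in a measure will be tested against its own baseline, and Supplementary Document 3, which could show whether items are shared, cannot be checked. A reader might infer that the analysis is planned. The documents do not support that; they only leave it open. This part of the objection stands and makes the point conditional.

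A reader might also infer that a study without a comparator can never separate regression to the mean from real differential change. That goes too far. The plan has three weekly follow-ups and a final visit after baseline, and the regression sentence itself refers to the study's progress. A trend across the later visits avoids baseline error.

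The highest false-significance rates need identical true change in everyone, which is implausible with pharmacotherapy and counselling, and no significance level is stated. The figure of 48 also allows for no loss after the start. Applying the earlier pilot's 79.5% retention as an illustration gives 48 x 0.795 = about 38 pairs and roughly 69 / 50 / 27% in place of 79 / 60 / 34%. These points qualify the rates. They leave the slope bias unchanged, because it depends on neither n nor the spread of true change.

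Finally, stable variance is an assumption. In general the slope is r x SD(post)/SD(pre) - 1, with r the pre-post correlation. If the spread grows enough, the sign can reverse. In the earlier pilot's exhaled CO (9.2 +/- 3.4 to 7.0 +/- 5.7 ppm, if these are SDs), it is negative only when r is below 3.4/5.7 = 0.60. CO is not listed as an outcome in section 7.

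**Conclusion.** The point holds as a minor, conditional one. The wording of 7b permits an analysis whose estimate is shifted by -(1 - R) from noise alone, given stable variances and true change unrelated to true baseline. The reliabilities are assumed, so -0.30 to -0.10 is an illustrative range. The false-significance rates are more fragile than the slope, running from 79% down to 10% for the regression across the settings tabulated.

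It would be wrong to conclude that the exploratory analyses as a whole are unsound. Sociodemographic and stressor factors, and different smoking measures with independent error, keep the nominal error rate. The primary feasibility endpoint is untouched, and nothing in the documents says that a relation between baseline and change will be read as differential benefit.

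**What to change.** Add to section 7b:

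> Change from baseline in a measure will not be tested against its own baseline value, strata of that value, or baseline items that form part of the same score. If shown, such results will be descriptive and not interpreted as differential benefit, because of regression to the mean. If the relation to own baseline is of interest, the trend across the post-baseline weekly visits, which does not include the baseline value, may be related to baseline as an exploratory analysis.

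Keep the planned t-test, ANOVA and regression for sociodemographic factors, stressors and different baseline smoking measures, and report estimates with 95% confidence intervals. Add a note that results for different smoking measures need cautious reading where their errors may be correlated with those of the outcome.

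The cost is a few sentences and no new data. The study gives up a formal test of baseline-to-final change on own baseline. The weekly-trend alternative has modest power, would miss a differential drop before week 1, and needs the same items asked over a comparable recall period at each visit.
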